1 INTRODUCTION

This is a modular Phase I/II, open-label, dose escalation and expansion, multicentre study that evaluates the safety, tolerability, pharmacokinetics (PK), and preliminary efficacy of AZD0466 as monotherapy or in combination with other anticancer agents in patients with advanced non-Hodgkin lymphoma (NHL).

This SAP provides a technical elaboration of the statistical analyses for all modules as outlined in the clinical study protocol. The SAP would be amended in future modules based on the module-specific protocol amendments to include AZD0466 in combination with other anticancer treatments.

This SAP should not be read in isolation but in conjunction with the clinical study protocol (CSP) and the case report form (CRF). The analyses described in this SAP are based upon the following study documents:

- CSP, Version 2.0 (Nov 01, 2021)
- Electronic Case Report Form (eCRF), version 1.0 (Jan 26, 2022)

Specifications for tables, figures, and listings are contained in a separate document.

[figure not shown]
2 STUDY OBJECTIVES - CORE

The objectives and endpoints for the core protocol are provided in [Table 1](#) below. Refer to the relevant individual modules for additional objectives and endpoints when applicable.

2.1 Objectives

Table 1 Objectives and Endpoints-Core

| Primary Objective | |
|--------------------------|---|
| | Endpoints/Variables |
| Part A | 
 Incidence of AEs and DLTs Changes from baseline in laboratory parameters, electrocardiograms, and vital signs |
| Part B | 
 ORR 
ORR is based on the revised response criteria for malignant lymphoma (Cheson et al 2014)
 |
| Secondary Objective | |
| | Endpoints/Variables |
| Part B | 
 Incidence of AEs and SAEs Changes from baseline in laboratory parameters, physical examinations, performance status, electrocardiograms, and vital signs |
| Part A and Part B | 
 Tumour response: 
 CR rate DoR TTR PFS OS 
Tumour response endpoints based on revised response criteria for malignant lymphoma (Cheson et al 2014)
 |
| Part A and Part B | 
 Plasma concentrations and derived PK parameters for study drug(s), to be specified for each module |

AE = adverse event; CCI [REDACTED] CCI [REDACTED]; B-NHL = B-cell non-Hodgkin lymphoma; CR = complete response; DLT = dose-limiting toxicity; DoR = duration of response; CCI [REDACTED]; MTD = maximum tolerated dose; ORR = objective response rate; OS = overall survival; PFS = progression-free survival; PK = pharmacokinetic(s); RP2D = recommended Phase II dose; R/R = relapsed/ refractory; SAE = serious adverse event; TTR = time to response.

3 CHANGES TO PROTOCOL PLANNED ANALYSES - CORE

Not Applicable.

4 DATA ANALYSIS CONSIDERATION - CORE

4.1 Timing of Analyses

For the timing of analyses, refer to the individual modules.

4.2 Analysis Populations

For the definitions of the analysis population refer to the individual modules.

4.3 General Considerations

4.3.1 Data Quality Assurance

All tables, figures and listings to be included in the report will be independently checked for consistency, integrity and in accordance with standard Parexel procedures.

4.3.2 General Presentation Considerations

No formal hypothesis testing is planned for this study.

Unless stated otherwise, each module and cohort will be analysed separately.

The below mentioned general principles will be followed throughout the study:

- Continuous endpoints are summarised by the number of observations, mean, standard deviation (Std Dev), median, upper and lower quartiles (as applicable), minimum, and maximum. For data that requires log-transformation, it is more appropriate to present geometric mean, coefficient of variation (CV), median, minimum and maximum. Categorical endpoints are summarised by frequency counts and percentages for each category.
- If data are available for less than 3 patients, no summary statistics other than minimum, maximum and number of observations are presented.
- Unless otherwise stated, percentages will be calculated out of the analysis set total, by dose level/cohort as appropriate.
- For continuous data, descriptive summary statistics (mean, median, Std Dev, standard error, confidence intervals [CIs]) will be rounded to 1 additional decimal place compared to the original data. Minimum and maximum will be displayed with the same accuracy as the original data.

- For categorical data, percentages will be presented to 1 decimal place.
- All CIs presented will be two-sided at the 95% level unless stated otherwise.
- SAS® version 9.4 (*as a minimum*) will be used for all analyses.

4.3.3 General Study Level Definitions

Baseline is the last non-missing value obtained prior to the first dose/administration of any study treatment and any information collected after first dose/administration of study treatment is regarded as post-baseline information. If two visits are equally eligible to assess patient status at baseline (e.g., screening and baseline assessments both on the same date prior to first dose/administration with no washout or other treatment in the screening period), the average is taken as the baseline value. For non-numeric laboratory tests (i.e. some of the urinalysis parameters) where taking an average is not possible then the best value is taken as baseline as this is the most conservative. In the scenario where there are two assessments on Day 1 prior to first dose, one with time recorded and the other without time recorded, the one with time recorded is selected as baseline. Where safety data are summarised over time, study day is calculated in relation to date of first treatment. For assessments on the day of first dose where time is not captured, a nominal pre-dose indicator, if available, serves as sufficient evidence that the assessment occurred prior to first dose. Assessments on the day of the first dose where neither time nor a nominal pre-dose indicator are captured is considered prior to the first dose if such procedures are required by the protocol to be conducted before the first dose. If no value exists before the first dose/administration, then the baseline value is treated as missing.

Change from baseline will be calculated as the post-dose value minus the baseline value as:

$$\text{post-baseline value} - \text{baseline value}$$

Percent change from baseline will be calculated as:

$$\frac{\text{post-baseline value} - \text{baseline value}}{\text{baseline value}} \times 100$$

Study day 1 is defined as the date of first dose of study treatment (Cycle 1 Day 1). For visits (or events) prior to first dose, study day is defined as (date of visit [event] – date of first dose of study treatment). For visits (or events) that occur on or after first dose of study treatment, study day is defined as (date of visit [event] – date of first dose of study treatment + 1).

For listings (such as for adverse events [AEs]) that include the derivation of “days since last dose” is defined as (event date – date of last dose) where “date of last dose” is defined as date of the most recent dosing immediately preceding the event occurrence. Thus, events

on the same day as the last dose will be described as occurring zero days from last dose of study treatment.

4.3.4 Visit Window

Visit windows will be defined for any presentations that summarize values by visit. The following conventions will apply:

- Visit windows will be exhaustive so that data recorded at any timepoint has the potential to be summarized. Inclusion within the visit window will be based on the actual date and not the intended date of the visit.
- The window for the visits following baseline will be constructed in such a way that the upper limit of the interval falls halfway between the 2 visits (the lower limit of the first post-baseline visit will be Day 2). If an even number of days exists between 2 consecutive visits, then the upper limit will be taken as the midpoint value minus 1 day.
 - Examples applicable to each module will be defined separately for that module.
- Visit windowing will be conducted up to and including the end of treatment visit. That is, the end of treatment visit will be reassigned a scheduled visit based on the study day the end of treatment visit occurred at.
- If there are more than one value per patient within a time window then the closest value to the scheduled visit date are summarised, or the earlier, in the event the values are equidistant from the nominal visit date. The listings highlight the value for the patient that contributed to the summary table, wherever feasible. Note: in summaries of extreme values, all post baseline values collected are used including those collected at unscheduled visits regardless of whether or not the value is closest to the scheduled visit date.
- For summaries at a patient level, all values are included, regardless of whether they appear in a corresponding visit based summary, when deriving a patient level statistic such as a maximum.
- Visit windowing will be done separately for each assessment based on the schedule of events specific to that assessment.
- Should Study Day be missing (due to partial or missing dates), then visit will be assigned to the nominal visit at which that assessment was recorded, and no windowing will be performed.
- For summaries showing the maximum or minimum values, the maximum/minimum values recorded while on study treatment will be used (regardless of where it falls in an interval).

- Listings should display all values contributing to a timepoint for a patient.
- If multiple measurements are taken on the same day, a measurement due to inappropriate procedures or any other issues with the first measurement, the reassessment measurement on that day will take preference for analysis, should the values for that day be in the analysis after visit windowing rules have been applied.

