Activated partial thromboplastin time (aPPT)		High-density lipoprotein (HDL)	Creatine kinase (CK)
Prothrombin time (PT)		Low-density lipoprotein (LDL)	
Fibrinogen		Pregnancy test (females of childbearing potential only)	
Viral Serology		Urine human chorionic gonadotropin (hCG)	Serum beta hCG
Hepatitis B and C	CMV	Others	
SARS-CoV-2		Serum immunoglobulins ^a	Beta-2 microglobulin ^a

^a At screening, at target dose (predose timepoint) and then as clinically indicated and at end of treatment visit.

^b Collected at screening, pre-infusion on each dosing day, and end of treatment visit.

Lipids: triglycerides, high density lipoprotein, low density lipoprotein, and cholesterol.

ACTH = adrenocorticotrophic hormone; ALT = alanine aminotransferase; AST = aspartate aminotransferase; BUN = blood urea nitrogen; CMV = cytomegalovirus; GGT = gamma-glutamyltransferase; LDH = lactate dehydrogenase; SARS-CoV-2 = severe acute respiratory syndrome coronavirus 2; TSH = thyroid-stimulating hormone; WBC = white blood cell.

NB. In case a patient shows an AST or ALT $\geq 3 \times$ ULN together with total bilirubin $\geq 2 \times$ ULN, refer to [Appendix E](#) for further instructions.

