5.6.4.2 Presentations

For all continuous laboratory assessments the absolute values and change in each parameter from baseline to each post-baseline visit will be summarised using descriptive statistics at each time point by dose level/cohort as appropriate. Graphical presentations using box plots

of absolute values and change from baseline values for haematology and clinical chemistry parameters will also be shown.

Laboratory abnormalities occurring from the start of IP administration to the last assessment on study will be presented. Worst toxicity grade, rates of grade 3-4 toxicity, and grade shifts of 2 or more from baseline to the maximum grade will be presented.

Summaries indicating hyper- and hypo- directionality of change will be produced, where appropriate. Laboratory parameters that cannot be graded via NCI Common Terminology Criteria for Adverse Events (CTCAE) will be summarised with frequencies of post-baseline laboratory values categorized as low (L), normal (N), or high (H) using laboratory normal ranges compared to baseline.

Listings will be provided for all laboratory results. Laboratory parameters will be assessed at baseline as well as throughout the study.

Also, a separate table for the changes in platelets and neutrophils will be summarised over time per dose level/cohort, as appropriate.

Liver Function Parameters

Number and percentage of participants with elevated post-baseline ALT, AST, or Total Bilirubin will be tabulated. Individual patient data where elevated ALT or AST plus total bilirubin fall into the “Potential Hy’s law” will be summarised and/or listed.

Following Safety Review Committee (SRC) review of emerging data additional laboratory safety assessment sample times may be added or removed if indicated by the emerging data. For presentation of the results this analysis plan will follow the initial time schedule for these parameters.

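### For seven laboratory tests scheduled after baseline only at Cycle 1 Day 8 and end of treatment, SAP 4.3.4 lets the pre-target-dose Day 8 value displace the end-of-treatment value from the by-visit tables

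*SAP*

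**What the plan says.** SAP 4.3.4 sets the windows for any output that summarises values by visit. Five of its rules act together:

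- Coverage: "Visit windows will be exhaustive so that data recorded at any timepoint has the potential to be summarized".
- Scope: "Visit windowing will be done separately for each assessment based on the schedule of events specific to that assessment".
- Start of the first window: "the lower limit of the first post-baseline visit will be Day 2".
- EoT: "the end of treatment visit will be reassigned a scheduled visit based on the study day the end of treatment visit occurred at".
- Several values in one window: "If there are more than one value per patient within a time window then the closest value to the scheduled visit date are summarised", with ties going to the earlier value.

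Seven tests carry footnote a in the laboratory table (Protocol Table 12, SAP Table 3): troponin I, BNP or NT-proBNP, cortisol, ACTH, TSH, serum immunoglobulins and beta-2 microglobulin. Their schedule is "At screening, at target dose (predose timepoint) and then as clinically indicated and at end of treatment visit". The schedules of activities agree, with screening and Day 8 in Cycle 1 and only EoT from Cycle 2 onward.

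SAP 5.6.4.2 then commits to the output concerned: "For all continuous laboratory assessments the absolute values and change in each parameter from baseline to each post-baseline visit will be summarised". It adds box plots for haematology and clinical chemistry; five of the seven tests are listed under clinical chemistry. Neither the SAP nor the protocol gives EoT a row of its own or exempts these tests.

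**The concern.** The Day 8 sample is drawn before the first target-dose infusion, when the patient has had only the ramp-up doses of Days 1 and 4. The EoT sample is the only scheduled one that follows a target dose. A rule that places both in one window and keeps the value nearer Day 8 retains the less informative value.

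Change from baseline in laboratory parameters and ECGs is a Part A primary endpoint and part of a Part B secondary one (SAP Table 1). Protocol Table 1 lists cardiovascular toxicity as an important potential risk. A troponin or BNP table with a single post-baseline row headed Cycle 1 Day 8 would therefore describe ramp-up only. Where Day 8 was missed, that row would also hold values taken months later. LVEF and ECG are scheduled sparsely enough to be partly exposed as well, and Protocol 8.2.5.1 uses the EoT scan to judge recovery after a T wave abnormality.

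**Working it through.** **Rule.** For scheduled days d1 < d2 < …, the first lower limit is Day 2. The upper limit of window i is the midpoint (d_i + d_(i+1))/2, rounded down, and reduced by 1 when the gap is even. The next window starts the day after. The last window is taken as open-ended. Within a window the value with the smallest |day − d_i| is chosen, ties to the earlier.

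**Reproducing the SAP's own figure (SAP 10.3.1, physical examination).** Scheduled days are 8, 15, 22, 29, 36, 43, 50, 57 and then 64. The midpoints are 11.5, 18.5, 25.5, 32.5, 39.5, 46.5, 53.5 and 60.5, so the windows are 2-11, 12-18, 19-25, 26-32, 33-39, 40-46, 47-53 and 54-60. All eight match.

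**The seven tests.** The only fixed post-baseline day is Day 8, so there is one window, from Day 2 with no upper limit.

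- With the Day 8 sample taken on Days 6 to 10 (the ±2-day visit window) and EoT on any later day up to Day 759, the day pairs number 753 + 752 + 751 + 750 + 749 = 3755.
- The EoT value is chosen in four: (Day 8 sample, EoT) on study days (6,7), (6,8), (6,9) and (7,8). It is displaced in 3755 − 4 = 3751.
- These are counts of day pairs, not probabilities. In every pair with EoT after Day 9, EoT is displaced.
- If the Day 8 sample is missing and EoT is on Day 170, the EoT value is tabulated as Cycle 1 Day 8, which is 170 − 8 = 162 days off.

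**Contrast: a weekly test.** For haematology, an EoT sample on Day 170 falls in the window of Cycle 7 Day 1 (28 × 6 + 1 = Day 169). The neighbouring visits are Days 162 and 176, the midpoints are 165.5 and 172.5, and the window is 166-172. The label is one day off.

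**ECG.** Scheduled days are Cycle 2 Day 1 = 29, Cycle 2 Day 8 = 36 and Cycle 4 Day 1 = 85. The midpoints are 32.5 and 60.5, so the Cycle 2 Day 8 window is 33-60. An EoT ECG on Days 37-60 is displaced when a Cycle 2 Day 8 value lies closer to Day 36.

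**LVEF.** Scheduled days are Cycle 2 Day 8 = 36 and Cycle 5 Day 8 = 28 × 4 + 8 = 120. The gap is 84 and the midpoint 78, so the upper limit is 77 (78 if the even-number rule counts the 83 days strictly between the visits). The window is Days 2-77.

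- EoT on Days 37-77 with an on-time Day 36 scan: displaced.
- EoT before Day 36 with no Cycle 2 scan: kept, but labelled Cycle 2 Day 8.
- EoT on Days 78-119 with no Cycle 5 scan: kept, labelled Cycle 5 Day 8.

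**The case against.** The best defence is that little is lost. Listings hold every value. SAP 5.6.4.2 presents laboratory abnormalities through to the last assessment on study, with worst grade, grade shifts and low/normal/high categories. SAP 4.3.4 keeps all post-baseline values for extremes and patient-level statistics. A raised EoT troponin or BNP could therefore still surface. This largely stands, so a reader should not infer that these values vanish from the report. It does not restore the by-visit change from baseline. SAP 4.3.4 is also not consistent on extremes: another bullet limits maxima and minima to values recorded on study treatment, and EoT is performed once treatment has been permanently discontinued.

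Three stronger readings are tempting, and the documents do not support them.

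- *The LVEF of early stoppers is dropped.* The earliest stoppers, with no Cycle 2 scan, keep their EoT value under a wrong label; only the cases shown above are displaced. SAP 5.6.10.2 does not promise a by-visit LVEF table.
- *The target-dose effect can never appear, because every EoT value goes.* A missing Day 8 value lets EoT in, mislabelled. A missing study day keeps the nominal visit. Clinically indicated samples may exist, although they fall in the same window and normally lose to Day 8.
- *The Part A laboratory endpoint as a whole is compromised.* Haematology and the main chemistry panel are sampled weekly, and their EoT values go to a nearby visit.

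It is also fair to say that the SAP states no upper limit for a last window and that table specifications sit in a separate document. The open-ended reading is an inference from windows that are exhaustive and that must receive EoT.

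**Conclusion.** The point holds for the seven tests. Applied as written, the rule gives them a single post-baseline row headed Cycle 1 Day 8. Almost every EoT value (3751 of 3755 day pairs) is displaced from that row when a Day 8 value exists, and EoT takes the row under the wrong label when it does not. This is a rule with an unintended result rather than a missing detail. The loss is confined to the by-visit absolute and change-from-baseline tables and the matching box plots. ECG is affected in part, and LVEF in part if it is tabulated by visit. The conclusion assumes an open-ended last window and no contrary instruction in the separate table specifications.

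**What to change.** Add to SAP 4.3.4: for tests scheduled after baseline only at Cycle 1 Day 8 and EoT, and for LVEF and ECG where tabulated by visit, EoT results are shown in a separate 'End of treatment' row; they neither compete for a scheduled visit nor take its label. Weekly-schedule tests can keep the present rule, which labels their EoT values close to the true study day.

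The Day 8 window should not be closed at Day 11 by analogy with SAP 10.3.1. That limit is the midpoint to a Day 15 physical examination, which these tests do not have. A closure would also conflict with the exhaustive-window rule and with SAP 4.3.5 on unscheduled visits.

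The cost is one sentence and one row per affected table, with no new data. The EoT row will mix study days, which its heading can state. Later clinically indicated samples would still fall in the Day 8 window, as now.

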4.3.5 Handling of Unscheduled Visits

All unscheduled visit data have the potential to be included in the summaries, based on the assignment of visit using visit windowing as described in Section 4.3.4. Unscheduled visits will be considered for summaries showing the maximum or minimum values recorded while on study treatment.

4.3.6 Multiplicity/Multiple Comparisons

Not Applicable.

4.3.7 Handling of Protocol Deviations in Study Analysis

Important protocol deviations are defined as those deviations from the protocol likely to have an impact on the perceived efficacy and/or safety of study treatment.

The following general deviation categories will be defined. These deviations will be reviewed and assessed on a case-by-case basis by AstraZeneca to determine importance. Deviations considered to be important will be listed and discussed in the clinical study report (CSR) as appropriate. All decisions on importance will be made ahead of database lock and will be documented prior to the analysis being performed.

- Patients who deviate from entry criteria per CSP (Deviation 1)
- No baseline Lugano assessments on or before the date of first dose (Deviation 2)
- Received prohibited concomitant medications or therapies (Deviation 3)
- Patients deviating from prescribed dosing regimen (Deviation 4)
- Missed visits, assessments, or treatments that, in the opinion of the investigator, were due to Corona virus disease 2019 (COVID-19) global pandemic, and where there was a significant effect on either completeness, accuracy and/or reliability of the patient's data, or the patient's rights, safety or wellbeing (Deviation 5)
- Deviation from Good Clinical Practice as determined by medical review (Deviation 6)

None of the deviations should lead to subjects being excluded from any analysis populations described in the SAP, unless otherwise specified. However, if a deviation is serious enough to have a potential impact on the primary analysis, sensitivity analyses may be performed. The need for such a sensitivity analysis will be determined following review

of the protocol deviations ahead of database lock and will be documented prior to the analysis being conducted.

A list of all protocol deviations will be reviewed and decisions regarding how to handle these deviations in the analyses will be documented by the study team physician, clinical pharmacology scientist and statistician prior to database lock.

4.3.8 Missing Dates

Generally, the imputation of dates is used to decide if an observation is treatment emergent for adverse events or concomitant medications. The imputed dates should not be used to calculate durations, where the results would be less accurate.

The following are the guidelines used when partial dates are detected in the study:

- For missing diagnostic dates (e.g., disease diagnosis), if the day and/or month are missing use 01 and/or Jan. If year is missing, put the complete date to missing
- For missing AE or concomitant medication start dates the following will be applied:
 - a. Missing day: Impute the 1st day of the month unless month is the same as month of first dose of study treatment then impute first dose date.
 - b. Missing day and month: Impute 1st January unless year is the same as first dose date then impute first dose date.
 - c. Completely missing: Impute first dose date unless the end date suggests it could have started prior to this in which case impute the 1st January of the same year as the end date.
 - d. Imputed start date should be no later than the end date.
- For missing AE or medication end dates, the following will be applied:
 - a. Missing day - impute the last day of the month unless both the month and the year are the same as the last dose date or the primary analysis data cut-off date then impute the last dose date or the primary analysis data cut-off date.
 - b. Missing day and month - impute 31st December unless the year is the same as the last dose date or the primary analysis data cut-off date then impute the last dose date or the primary analysis data cut-off date.
 - c. Completely Missing – need to look at whether the AE/medication is still ongoing before imputing a date and also when it started in relation to study drug. If the ongoing flag is missing then assume that AE is still present / medication is still being taken (i.e. do not impute a date). If the AE/medication has stopped and start date is prior to first dose date then impute first dose date. Or if it started on or after first dose date then impute a date that is after the last dose of study drug date.
- Flags will be retained in the datasets indicating where any programmatic imputation has been applied, and in such cases, any durations would not be calculated.

- If a patient is known to have died where only a partial death date is available then the date of death is imputed as the latest of the last date known to be alive +1 from the database and the death date using the available information provided and applying the following:-
 - For Missing day only – using the 1st of the month.
 - For Missing day and Month – using the 1st of January.

